2.0 Rationale and Specific Aims

Rate of displacement following cast/splint application has been studied and varies between 21-39% based on the meta-analysis by Sengab et al. This randomized pilot study will include roughly 50-100 patients and will be completed in approximately 1 year with preliminary results available at that time. Between the 8 physicians and 4 nurse practitioners on staff within the pediatric orthopaedics department, approximately 20 patients weekly are seen who would meet eligibility for study participation. Assuming a 10% successful recruitment rate, it would require 6 months to recruit the desired number of participants. Eligible patients will be offered study inclusion during the initial outpatient clinic visit. These patients typically present to the clinic 3-7 days following injury.

The primary aim of this study is to determine whether activity influences loss of reduction of forearm fractures. Secondary aims of this study may provide insight to many other related questions as seen below:

- Does increased activity lead to more complications.
- Do instructions given to families influence activity level and do patients/families accurately report activity levels?
- Does activity level affect recovery length time of forearm fractures based on x-ray findings?

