5.0 Enrollment/Randomization

General inclusion/exclusion criteria will be used to determine patient eligibility. All eligible patients will be identified when they present to Vanderbilt's pediatric orthopedic clinic based on the clinicians interpretation of their presenting x-rays.

Consent is obtained during the office visit on paper or by REDCap econsent. Patients and families will be given as much time as they need to review the documents and ask questions. The patient consent process will be conducted using a REDCap-based electronic consent form or a paper consent form. The consent form has been developed in REDCap, a secure, web-based, HIPAA-compliant, data collection platform with a user management system allowing project owners to grant and control varying levels of access to data collection instruments and data (e.g. read only, de-identified-only data views) for other users.

If a patient decides to participate in the study, they will randomized to one of two groups: Group A and Group B. Patients will be randomly assigned to one of groups based on the date of enrollment. If the date of enrollment is an odd integer, they will be placed in Group A. If the date is an even integer, they will be placed in Group B.

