6.0 Study Procedures

The procedure studies will be as followed:

- Once non-operative management is deemed appropriate based on review of imaging and shared decision making with the family, eligible patients will be offered study participation during initial presentation at outpatient clinic visit (about 3-7 days post-injury). At the initial visit:
 - Standard or care X-rays will be reviewed
 - As part of standard of care a cast will be applied (or overwrapped with fiberglass)
 - Some participants will be provided an activity monitoring, based on availability, to be worn on the uninjured wrist or ankle consistent with manufacturers recommendations for the duration of casting treatment.
 - Participants will be randomized into restricted activity vs full activity groups and be read a respective standardized script regarding activity limitations. The same guidance will also be provided in the after visit summary (AVS).
 - Basic data will be collected including patient age, sex, BMI, initial displacement measurements, and other pertinent fracture characteristics easily obtainable from review of present radiographs.
- Patients will follow up at standard of care 1-2 week intervals for alignment checks. At these visits:
 - If the participants was provided a tracker, data from the monitoring devices will be imported with only a study id and date of birth to identify the patient. All data on the device will be deleted when information is imported.
 - Repeat standard of care x-rays will be obtained to assess for loss of reduction (defined as any change in angulation >10 degrees compared to initial reduction).
 - Incidence of complications such as unplanned cast changes, excessive skin irritation, cast wedging, loss of reduction, and operative management will be recorded.
 - For all enrolled patients, regardless of use of activity monitoring device, a validated Pediatric Activity Survey will be provided at follow-up appointments.
- Following all data collection, patient, survey, and activity tracker data will be analyzed

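### No usual-activity measure from before the injury is scheduled, so the comparison of activity between instruction groups cannot adjust for it

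*Protocol*

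**What the plan says.** Activity plays two parts in the protocol. In section 2.0 it is the exposure: "The primary aim of this study is to determine whether activity influences loss of reduction of forearm fractures". In the same section it is also an outcome of the randomized instruction: "Do instructions given to families influence activity level and do patients/families accurately report activity levels".

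Section 6.0 sets out what is measured and when:

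- **Initial visit, baseline data:** "Basic data will be collected including patient age, sex, BMI, initial displacement measurements, and other pertinent fracture characteristics easily obtainable from review of present radiographs". No activity item is named, although the list is open-ended.
- **Initial visit, monitor:** "Some participants will be provided an activity monitoring, based on availability, to be worn on the uninjured wrist or ankle". It is worn while the child is in the cast.
- **Follow-up visits, survey:** for all enrolled children, "a validated Pediatric Activity Survey will be provided at follow-up appointments". Neither its items nor its recall period are described.

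On when the initial visit falls, section 2.0 says "These patients typically present to the clinic 3-7 days following injury". Section 5.0 gives the allocation: "Patients will be randomly assigned to one of groups based on the date of enrollment", with odd dates going to Group A and even dates to Group B. The planned size is 50-100 in section 2.0 and 100 in section 12.0.

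**The concern.** Every scheduled activity measurement falls after the injury, and the survey comes only after the family has heard its script. Children aged 8 to 18 are likely to differ a good deal in how active they usually are. Without a starting value, all of that variation stays in the comparison of in-cast activity between the two instruction groups.

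The scripts in Appendix A add to the difficulty. Group B families are told that the child need not become more active, and Group A families are asked to limit certain activities. Both are framed against the child's own habits. A habitually quiet child in Group B may look restricted, and one in Group A may look adherent, with nothing recorded to tell the difference.

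Allocation by calendar date is predictable to anyone enrolling patients. One would therefore want to see whether the groups were alike in prior activity, and the plan gives no means to do so.

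In the primary analysis activity is observed, not randomized. Children who are active in the cast may differ in other ways from those who are not. This cannot be left to the statistical analysis plan, because no analysis can use a variable that was not collected.

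**Working it through.** **Is there a pre-injury measure anywhere?** The protocol has three possible sources.

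| Source | Who | When | Can it give pre-injury activity? |
|---|---|---|---|
| Survey | All | Follow-up visits | Not as described; recall period not stated |
| Monitor | Some, by availability | From the initial visit, about 3-7 days after injury | No |
| Baseline data | All | Initial visit | No activity item named |

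No other section of the text at hand schedules one.

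**Gain when activity is the outcome (instruction aim).** The protocol states no power, effect size, standard deviation or correlation, so there is no figure of its own to reproduce. The following is an illustration. Assume a continuous survey score, equal groups, and correlation r between the pre-injury and in-cast scores. Adjusting for the former multiplies the residual variance by 1 - r², and the equivalent sample size is N/(1 - r²).

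| r (assumed) | Variance removed, r² | Equivalent N, 100 enrolled | Equivalent N, 50 enrolled |
|---|---|---|---|
| 0.2 | 4% | 100/0.96 = 104 | 50/0.96 = 52 |
| 0.3 | 9% | 100/0.91 = 110 | 50/0.91 = 55 |
| 0.4 | 16% | 100/0.84 = 119 | 50/0.84 = 60 |
| 0.5 | 25% | 100/0.75 = 133 | 50/0.75 = 67 |
| 0.6 | 36% | 100/0.64 = 156 | 50/0.64 = 78 |

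The same gain can be read as a detectable difference. With two-sided alpha 0.05 and 80% power (both assumed), and n per group, the smallest detectable difference in SD units is (1.960 + 0.842) × √(1 - r²) × √(2/n).

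- N = 100 (n = 50): 2.802 × 0.200 = 0.56 SD unadjusted; × √0.96 = 0.55 at r = 0.2; × √0.64 = 0.45 at r = 0.6.
- N = 50 (n = 25): 2.802 × 0.283 = 0.79 SD unadjusted; 0.78 at r = 0.2; 0.63 at r = 0.6.

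**When activity is the exposure (primary aim).** Here the covariate is correlated with the exposure. If prior activity has no effect of its own on loss of reduction, conditioning on it removes a share r² of the exposure's variation and multiplies the standard error by about 1/√(1 - r²). At r = 0.4 this is 1.09, and at r = 0.6 it is 1.25. One hundred children then carry the information of about 84 (100 × 0.84) or 64 (100 × 0.64). Adjustment in this analysis is a guard against confounding and may cost precision.

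**What a balance check could show.** With equal groups, the standard error of the difference in mean prior activity is √(2/n) SD: 0.20 at N = 100 and 0.28 at N = 50. Chance alone gives differences up to about 1.96 × 0.20 = 0.39 SD or 1.96 × 0.283 = 0.55 SD in 95% of trials. The check would reveal a gross imbalance, not a small one.

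**Recall distance.** With the visit 3 to 7 days after injury, the week before injury ends 3-7 days back and begins 10-14 days back. The recalled period thus lies roughly 3 to 14 days before the visit.

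**The case against.** The strongest reply is that this is a self-described pilot with no stated power target, that nothing in the protocol is misstated here, and that a covariate is an improvement and not a condition of validity. That is largely right. The comparison of the two groups on loss of reduction does not need prior activity to be valid.

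Three stronger readings are tempting, and the document does not support them.

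- *Prior activity is the best predictor of activity in the cast.* Nothing in the protocol says how well it predicts. The cast and the Group A script may themselves disturb habits, so a low r is plausible, and at r = 0.2 the gain is small.
- *Prior activity will never be recorded.* The baseline list is open-ended and the survey's items and recall period are not described. The contents also name a procedure calendar that is not in the text at hand. What can be said is that no such measure is scheduled in what is shown.
- *The precision gain applies to the primary aim.* It does not, as the calculation for activity as exposure shows. The route by which habitual activity might confound that analysis, for example through more forceful injuries, is conjecture. Initial displacement, which section 3.0 cites as a risk factor and section 6.0 collects, may already capture part of it.

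Two practical objections also stand. The recall reaches back up to two weeks and may not match the window for which the survey was validated. And because allocation follows the date, completing the form before the group is known must be arranged; it cannot be assumed. A balance check would also not cure the predictability of the allocation, which is a separate matter.

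**Conclusion.** The point holds in a limited form. As written, no usual-activity measure from before the injury is scheduled, and neither the follow-up survey as described nor the monitor can supply one. Two things are lost: adjustment for usual activity when in-cast activity is compared between the instruction groups, and any check of balance in prior activity under odd/even-date allocation.

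For the first, the loss is between 4% and 36% of the variance if r lies between 0.2 and 0.6. That range is assumed, and the result depends wholly on it. It applies at full sample size to survey scores only, since monitor data will exist for only some children. For the primary analysis the missing variable is a possible confounder of unknown importance, and no precision gain should be claimed. This is a cheap improvement worth making before enrolment, not a flaw that invalidates the randomized comparison.

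**What to change.** Add one administration of the same survey to the initial visit in section 6.0, worded to ask about the usual week before the injury. State that it is completed after consent but before the group is disclosed and the script is read. Confirm from the survey's documentation whether it may be used with that recall period, and if not, note the departure.

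In the analysis:

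- Use the score as a covariate when in-cast survey activity is compared between the instruction groups.
- Describe it by group as a check of balance.
- In the analysis of activity against loss of reduction, treat it as a possible confounder alongside initial displacement, for instance in a sensitivity analysis, with results shown with and without it.

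The cost is one short form at a visit that already takes place, plus recall error. No visit is added and care does not change.

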7.0 Risks

Given that there is not standardized or accepted activity recommendation for these patients, this study will not put these patients at increased risk of further injury. Further, the activity recommendations for the “unrestricted activity” group has common-sense exceptions on what the patient is allowed to do to prevent further injury such as avoidance of high risk situations such as contact sports. The devices are safe and usually well tolerated and have been validated for use in children. Minor possibility of skin irritation from the activity tracker due to chronic use however the device can easily be taken off if this is a problem. There are no other identifiable risks pertaining to the activity monitors or the activity restriction guidelines for providers, patients, or families.

Because patient data is being collected there is a slight risk of a breach of confidentiality. To reduce this risk, this study will utilize the REDCap platform for data collection and management. This project will utilize the REDCap platform for data collection and management. Project team

members listed as Key Study Personnel with existing electronic health record (EHR) system access rights may also be granted use of REDCap Clinical Data Interoperability Services (CDIS) tools. These tools are designed to enable transfer of relevant study-related data from the Vanderbilt Research Derivative and/or directly from the EHR into REDCap.

Only research personnel will have access to the patient's study information to ensure confidentiality. Any data sent to non-key study personnel for statistical analysis will be deidentified (dates will be shifted using a REDCap feature. The data obtained and stored in Redcap will only be accessible by research personnel. Any physical study forms (ex. Consent documents, surveys) will be kept in a locked cabinet in the principal investigator's office]. All study data will be maintained for 6 years following study completion. Following this 6 year period, the Redcap database will be archived, electronic files will be permanently deleted and all physical study forms will be disposed of in shred-it confidentiality bins provided by VUMC. This research may benefit patients in the future by allowing surgeons to provide more appropriate, evidence-based counseling to patients and families to prevent further injury/complication

8.0 Reporting of Adverse Events or Unanticipated Problems involving Risk to Participants or Others

All adverse events related to this study should be reported to the principal investigator immediately. The principal investigator will then ensure prompt reporting to the IRB based on policy number III.L.

9.0 Study Withdrawal/Discontinuation

Patients will be asked to contact study personnel if they decide they no longer want to participate in the study. Once a patient has withdrawn their consent, no further study data will be collected on them, and all data that has been collected up until the point their consent was rescinded will be destroyed.

If the patient refuses or withdraws from the study, they will continue receive routine care with normal follow up appointments consistent with standard practice.

Patients may be withdrawn from the study for lack of compliance wearing the activity monitor.

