12.0 Follow-up and Record Retention

The duration of this study will last until we have enrolled 100 patients and will continue 3-4 months after the last patient is enrolled to ensure fracture healing is complete and any potential complications are captured. No additional research related follow up visits are required as part of this proposed study. Patients will follow at routine intervals regardless of study participation. All study data will be maintained for 6 years following study completion. Following this 6 year period, the Redcap database will be archived, electronic files will be permanently deleted, and all physical study forms will be disposed of in shred-it confidentiality bins provided by VUMC.

Appendices:

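### Section 9.0 lets staff withdraw randomized patients from the whole study for not wearing a monitor that only some receive and that the x-ray, complication and survey outcomes do not need

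*Protocol*

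**What the plan says.** Section 9.0 (Study Withdrawal/Discontinuation) ends with: "Patients may be withdrawn from the study for lack of compliance wearing the activity monitor". What the patient leaves is the study, not the monitoring part of it. No minimum wear time is given, and nothing is said about follow-up after such a withdrawal.

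Section 6.0 (Study Procedures) describes what the monitor is needed for:

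- Who gets one: "Some participants will be provided an activity monitoring, based on availability".
- The x-ray outcome: "Repeat standard of care x-rays will be obtained to assess for loss of reduction". Complications are recorded at the same visits.
- The survey: "For all enrolled patients, regardless of use of activity monitoring device, a validated Pediatric Activity Survey will be provided at follow-up appointments".

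Section 12.0 adds: "Patients will follow at routine intervals regardless of study participation". Section 7.0 says of skin irritation from the tracker that "the device can easily be taken off if this is a problem". One secondary aim in Section 2.0 asks: "Do instructions given to families influence activity level".

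**The concern.** Every participant is randomized to an activity script, and most of the data do not depend on the device. Not wearing the monitor leaves a gap in the monitor data and nowhere else, yet the rule permits removing the patient altogether.

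Non-wear arises after randomization. The scripts in Appendix A tell each family which group the child is in, so wearing the device could be related to group or to how active the child is. The documents do not show such a link, and its size and direction are unknown. If it exists, discretionary removal takes x-ray outcomes, complications and surveys out of the comparison by assigned group for reasons tied to group or outcome. An SAP can define analysis sets, but it cannot reliably restore outcomes that were not collected.

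Section 7.0 adds an ambiguity. It foresees taking the device off for skin irritation, and nothing says whether that counts as lack of compliance under Section 9.0.

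**Working it through.** **Comparison of the provisions.** The protocol states no monitor share, non-wear rate or dropout rate, so there is no figure of its own to reproduce. The point rests on setting two kinds of patient side by side under Section 6.0:

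| | Never given a monitor | Given one, does not wear it |
|---|---|---|
| Randomized script | yes | yes |
| X-rays for loss of reduction | yes | yes |
| Complications at visits | yes | yes |
| Activity survey | yes | yes |
| Monitor data | no | no |
| Can be withdrawn under the Section 9.0 rule | no | yes |

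The available data are the same; only the exposure to withdrawal differs.

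**Illustration of size.** Inputs from the protocol:

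- 100 patients, the enrolment target in Section 12.0. Section 2.0 says roughly 50-100.
- Risk of loss of reduction 30%, the midpoint of the 21-39% in Section 2.0: (21 + 39)/2 = 30.

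Assumptions:

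- 50 patients per group, and no true difference between groups.
- Share monitored *m*, non-wear among the monitored *w*, and risk in non-wearers *pn*.
- Every non-wearer is withdrawn and their outcomes are not recorded.

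A fraction *m·w* of each group is removed, so the risk among those kept is

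(0.30 − m·w·pn) / (1 − m·w).

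Central case, *m* = 0.5, *w* = 0.10 in A and 0.30 in B, *pn* = 0.45:

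- Group A: (0.30 − 0.05 × 0.45)/0.95 = 0.2775/0.95 = 0.2921; kept 50 × 0.95 = 47.5.
- Group B: (0.30 − 0.15 × 0.45)/0.85 = 0.2325/0.85 = 0.2735; kept 50 × 0.85 = 42.5.
- Difference B − A: 0.2735 − 0.2921 = −0.0186, or −1.9 points. Lost: 2.5 + 7.5 = 10 of 100.

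Variants by the same formula:

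| m | w in A / B | pn | Risk kept, A / B | B − A (points) | Lost of 100 |
|---|---|---|---|---|---|
| 0.25 | 0.10 / 0.30 | 0.45 | 0.296 / 0.288 | −0.8 | 5 |
| 0.50 | 0.10 / 0.30 | 0.45 | 0.292 / 0.274 | −1.9 | 10 |
| 0.75 | 0.10 / 0.30 | 0.45 | 0.288 / 0.256 | −3.1 | 15 |
| 0.50 | 0.10 / 0.20 | 0.45 | 0.292 / 0.283 | −0.9 | 7.5 |
| 0.50 | 0.20 / 0.20 | 0.45 | equal | 0 | 10 |
| 0.50 | 0.10 / 0.30 | 0.30 | 0.300 / 0.300 | 0 | 10 |
| 0.50 | 0.10 / 0.30 | 0.15 | 0.308 / 0.326 | +1.9 | 10 |

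Differences are taken before rounding.

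Standard error of the difference in the central case: √(0.292 × 0.708/47.5 + 0.274 × 0.726/42.5) = 0.095. With all 100 kept it is √(2 × 0.30 × 0.70/50) = 0.092.

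If only 50 patients are enrolled, half monitored and 20% of those not wearing the device, the rule removes 50 × 0.5 × 0.2 = 5.

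**The case against.** The strongest reply is that the harm is inferred. The rule says patients may be withdrawn, not that they must be, and the protocol is silent on whether outcomes are still recorded afterwards. The clause that "all data that has been collected up until the point their consent was rescinded will be destroyed" is written for withdrawn consent and does not mention withdrawal by the study team. X-rays are standard of care, visits continue regardless, Section 10.0 names patient charts as a data source, and Section 7.0 describes transfer from the health record into the study database. Images and clinical complications would therefore largely exist in the chart.

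Much of this stands: the data-destruction clause is not part of this point, and x-rays may well survive. But their existence in a chart does not establish that the study may use them after the patient has been withdrawn, and a survey that was never given is lost. Discretion without a criterion, exercised after the group is known, offers less protection than a fixed rule.

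A second reply is that monitor data serve the primary aim, and non-wearers lack them anyway. That is correct for any analysis by monitor-measured activity. It justifies leaving non-wearers out of that analysis only. The protocol itself enrols patients without a monitor, so monitor data are not a condition of taking part.

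Third, the illustration uses assumed inputs throughout, takes the upper end of the planned sample size, and gives zero under equal non-wear or equal risk. That is also correct. It shows what is possible, not what is likely. Finally, removal for skin irritation would not ordinarily be read as non-compliance; it is a missing definition, not a contradiction.

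**Conclusion.** The concern holds and should be fixed. The withdrawal rule does not fit the study's own design: it permits discarding randomized patients who can supply every outcome that a patient without a monitor supplies. This follows from the text alone and does not depend on the illustration.

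The consequence is uncertain and probably modest. Under the assumptions shown, with 100 patients and unequal non-wear, 5 to 15 patients are lost and the spurious difference runs from 0.8 to 3.1 points in either no particular or a reversible direction, depending on the risk in non-wearers. Even the largest value is about a third of the standard error of 9.5 points. The patient loss occurs even where the bias is zero, provided withdrawn patients' outcomes are not recorded. What is affected is the comparison by assigned group, the complication counts and the survey analyses; analyses of monitor-measured activity are not.

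**What to change.** Delete the non-compliance sentence in Section 9.0 and state instead that:

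- not wearing the monitor, including removal for skin irritation, makes monitor data missing and nothing else;
- the patient stays in follow-up for x-rays, complications and the survey, and is analysed in the assigned group;
- a definition of valid wear time applies only to analyses of monitor data.

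The cost is one replaced sentence through a protocol amendment. No visit is added, because patients attend routine follow-up anyway.
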